11.0 Subject Disposition

The number and percentage of subjects randomized, dosed in Period 1, 2, 3 and 4, included in the SAF, in the PDAS, completing the study, withdrawing from the study prematurely and a breakdown of the corresponding reasons for withdrawal will be presented by treatment sequence and overall. The denominator for the percentage is the number of subjects randomized.

12.0 Protocol Deviations and Violations

Protocol deviations/violations will be included in the CSR.

13.0 Demographic and Baseline Characteristics

13.1 Demographics

All demographic data as collected during the screenings visit will be listed by subject.

Subject demographics will be summarized descriptively overall. The summary will include the subjects' age (in years), gender, race, ethnicity, weight (in kg), height (in cm), and body mass index (BMI) (in kg/m²). Demographics will be summarized for the SAF and PDAS (if different).

13.2 Medical History

Medical history will be listed.

13.3 Other Baseline Characteristics

The results of drug and alcohol screen at screening will be listed.

Serology (Hepatitis B surface antigen, Hepatitis C antibody and human immunodeficiency virus) will be listed.

Pregnancy (beta subunit of human chorionic gonadotropin) will be listed.

14.0 Concomitant Medications

Concomitant medication will be listed. Medications are categorized by data management as prior or concomitant. This information will also be listed.

Concomitant medications will be coded according to the World Health Organization – Drug Dictionary Enhanced (WHO-DDE) (Version Global B3 2018Sep01 or later).

15.0 Treatment Compliance and Exposure

Exposure data will be listed by subject.

16.0 Pharmacokinetic Analyses

Samples are collected at pre-dose, and at 3 h (the estimated t_{max}) and 24 h post-dose. PK parameters will not be derived.

16.1 Pharmacokinetic Variables

PK concentrations of LY3526318 and the main (active) metabolite M6 will be analyzed in plasma.

16.2 Pharmacokinetic Summaries

Plasma concentrations for LY3526318 and M6 BQL will be set to ½ lower limit of quantification (LLOQ) in the computation of mean concentration values. Descriptive statistics (number of subjects, arithmetic mean, SD, coefficient of variation (CV), geometric mean, geometric CV, median, minimum, and maximum) will be used to summarize the plasma concentrations by treatment at each scheduled time point. If over ½ the subjects for a specific combination of time point, treatment and analyte have values BQL then the descriptive statistics of that specific combination will not be presented and will instead display as BQL for the mean and minimum. With the exception of maximum all other statistics will be missing.

All individual subject plasma concentration data will be listed together with the descriptive statistics.

17.0 Pharmacodynamic Analysis

17.1 Pharmacodynamic Variables

PD assessments will be DBF measured by two methods, LDI and LSCI. For time points with a pre- and post-CA measurement available, the percentage change will be calculated.

17.2 Pharmacodynamic Summaries

17.2.1 Descriptive Summary

The individual DBF measurements absolute values (all 5 time points) and percentage change from pre-CA (for post-CA at 3 and 24 hours post study drug) will be listed and summarized descriptively by treatment, timepoint, CA concentration and method.

The individual percentage change from pre-CA will be graphically presented with the treatments combined in a plot by subject, CA concentration and method. Additionally, combined individual plots will be presented, with all individual percentage change combined in a plot by treatment, CA concentration and method. The arithmetic mean (\pm SD) will be graphically presented with the treatments combined in a plot, by CA concentration and method.

17.2.2 Statistical Analysis

An analysis of variance (ANOVA) will be performed on the percentage change (pre- to post-CA) at time points 3 h and 24 h post-dose using PROC MIXED in SAS. The percentage change will be used untransformed in the analysis. The model will include fixed effects for treatment, period, sequence, time and treatment*time interaction and a random effect for subject within sequence. The analysis will be done for each, method and CA concentration separately. From this model the least-squares means (LSMeans) for each treatment (including placebo) and the difference of the LSMeans for each of the active treatments with placebo at 3 h and at 24 h post-dose and the corresponding P value will be estimated for each method and CA concentration.

In the summary of the statistical analysis, it will be indicated that the result for LDI, 3 hours post-dose is the primary end point.

In SAS code:

```

proc mixed data=dbf;
  by CAconc method;
  class subject trtan time           period seq;
  model pchg = trtan time trtan*time period seq;
  random subject(seq);
  lsmeans trtan*time ;
  /*estimates*/
run;
quit;

```

For each of the active dose levels and CA concentrations, a decrease relative to placebo of the percentage change (pre- to post-CA) with a P value below (0.05/3) will be considered statistically significant.

Additionally, the same model (with fixed effects for treatment, period, sequence, time and treatment*time interaction and a random effect for subject within sequence) will be applied to the absolute values for each method and CA concentration separately, using data from all time points (i.e. pre study drug, 3 h pre- and post-CA, 24 h pre- and post-CA). From this model, using the absolute values, LSMeans and the differences with 90% CI and P-value will be estimated for each method and CA concentration for the following comparisons:

#	LSMean (absolute value) of	Compared with LSMean (absolute value) of
1	D1 post-CA at 3 h	Placebo post-CA at 3 h
2	D2 post-CA at 3 h	Placebo post-CA at 3 h
3	D3 post-CA at 3 h	Placebo post-CA at 3 h
4	D1 post-CA at 24 h	Placebo post-CA at 24 h
5	D2 post-CA at 24 h	Placebo post-CA at 24 h
6	D3 post-CA at 24 h	Placebo post-CA at 24 h
7	Placebo pre-CA at 3 h	Placebo pre study drug at 0 h
8	D1 pre-CA at 3 h	D1 pre study drug at 0 h
9	D2 pre-CA at 3 h	D2 pre study drug at 0 h
10	D3 pre-CA at 3 h	D3 pre study drug at 0 h
11	Placebo pre-CA at 24 h	Placebo pre study drug at 0 h
12	D1 pre-CA at 24 h	D1 pre study drug at 0 h
13	D2 pre-CA at 24 h	D2 pre study drug at 0 h
14	D3 pre-CA at 24 h	D3 pre study drug at 0 h

In SAS code:

```

proc mixed data=dbf;
  by CACconc method;
  class subject trtan time           period seq;
  model aval = trtan time trtan*time period seq;
  random subject(seq);
  lsmeans trtan*time ;
  /*estimates*/
run;
quit;

```

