9.6. Pharmacodynamics

9.6.1. *Dermal Blood Flow (DBF) Measurements by Laser Doppler Imaging (LDI) and Laser Speckle Contrast Imaging (LSCI)*

Dermal blood flow will be measured at visits and time points as specified in the Schedule of Activities (Section 2). All measurements for assessment should be performed while the participants are resting in a supine position on a comfortable bed in a quiet, ambient temperature-controlled room after at least 30 minutes acclimatization period.

Measurements of DBF will be taken with or without the application of a reactive agent to the skin. Based on the presumptive mechanism of action for LY3526318, CA will be used as the reactive agent to induce DBF.

Two methods will be used to measure DBF at each time point: DBF measurements from LDI (PeriScan PIM 3 system, Perimed, Stockholm, Sweden) and LSCI (PeriCam PSI System, Perimed, Stockholm, Sweden). The LDI assessment will be performed following LSCI assessment. The screening LDI measurements will be used to determine study eligibility.

Given that an upper extremity (forearm) requires approximately 5-days to recover from a reactive DBF measurement, the schedule between the screening and first study drug administration should account for this frequency limitation. During the first period, the extremity used for the first post-dose DBF measurements is chosen and the contralateral forearm

will be used for the 24-hour post-dose time point. Subsequent study periods should use the same schedule of DBF based on forearm and time point.

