10.3.3. Pharmacodynamic Analyses

The primary endpoint is the percent change from pre-CA to CA-induced DBF as measured by LDI, compared to placebo at 3 hours post-dose. Summary statistics for each cohort will be provided by treatment. Mixed-effect model for repeated measure (MMRM) will be used to evaluate the primary endpoint including covariates such as treatment, period, carry-over, and sequence. Similar analyses will also be conducted for LDI at 24 hours post dose as well as DBF outcomes as measured by LSCI (laser speckle contrast imaging) at 3 hours and 24 hours.

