3.0 Introduction

This Statistical Analysis Plan (SAP) describes the statistical methods that will be used during the analysis and reporting of data collected under Eli Lilly and Company Protocol J2D-MC-CVAB(a).

This SAP should be read in conjunction with the study protocol and electronic case report form (eCRF). This version of the plan has been developed using the protocol dated 15-Nov-2019 (including all amendments up to this protocol date) and the final eCRF(s) dated 03-Jan-2020.

An approved and signed SAP is a requirement for database lock. An approved SAP is also required for unblinding of the study treatments.

This SAP only covers the results that will be processed by the PRA Early Development Services (EDS) Biostatistics Department.

PRA EDS will perform the pharmacokinetic (PK), pharmacodynamic (PD), and safety and tolerability evaluation.

This SAP supersedes the statistical considerations identified in the protocol; where considerations are substantially different, they will be so identified. Any post-hoc or unplanned analyses, or significant changes from the planned analysis in this SAP performed to provide results for inclusion in the clinical study report (CSR) but not included in this SAP, will be clearly identified in the CSR. Changes to planned analyses do not require an updated SAP but should be included in the CSR if significant.

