6.1 Sample Size Considerations

The sample size is justified based on the statistical power to meet the primary endpoint of DBF measurements from LDI assay at t_{max} . The power calculation used 10% CA-induced absolute DBF in comparison between LY3526318 and placebo arms. For a 20% reduction in DBF (assuming mean observed placebo DBF of 444.3 arbitrary perfusion units (PU) with standard deviation (SD) of 55.1 PU) and a significance level of 0.05, a paired t-test with 16 patients results in 98% power to reject the null hypothesis. Incorporating a Bonferroni adjustment to account for multiplicity (changing the significance level to 0.05/3) lowers the power slightly to 96%.

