7.0 Overview of Planned Analysis

7.1 Changes from Protocol

There are no changes from the protocol.

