9.4.3 Hypothesis Testing

Significance testing will be 1-sided at the significance level of 0.05/3 for the primary statistical analysis.

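### The primary 3 h test takes its error term from 3 h and 24 h values on opposite forearms, so its standard error rests on variance assumptions that the documents do not support

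*SAP*

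**What the plan says.** SAP 17.2.2 analyses the percentage change from pre- to post-cinnamaldehyde at 3 h and 24 h in one PROC MIXED call, run separately by method and cinnamaldehyde concentration. "The model will include fixed effects for treatment, period, sequence, time and treatment*time interaction and a random effect for subject within sequence". The code has one RANDOM statement, `random subject(seq)`. It has no REPEATED statement, no participant-by-time or participant-by-period term, and no separate residual variances by time. The 3 h LDI comparison from this model is the primary result. SAP 9.4.3 sets the test: "Significance testing will be 1-sided at the significance level of 0.05/3 for the primary statistical analysis".

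Protocol 9.6.1 fixes the forearm. In period 1 "the extremity used for the first post-dose DBF measurements is chosen and the contralateral forearm" is kept for 24 h, and "Subsequent study periods should use the same schedule of DBF based on forearm and time point". Within a participant, forearm and time are therefore the same factor in all four periods.

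For planning, SAP 6.1 assumes a "mean observed placebo DBF of 444.3 arbitrary perfusion units (PU) with standard deviation (SD) of 55.1 PU" and a 20% reduction, on the absolute scale. Neither document gives a percentage-change SD, a left-right difference or any other variance component.

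**The concern.** A pooled error term is harmless when it estimates the true variance of the contrast being tested. Here it need not. A participant whose two forearms react differently adds a stable difference between 3 h and 24 h. That difference cancels from the 3 h comparison of dose with placebo, because all four 3 h values come from the same arm, but the model has nowhere to put it except the residual. Variation shared by both times within a period, or unequal variances at the two times, also separates the pooled residual from the variance the contrast needs. At stake is the calibration of three tests at 0.05/3: lost power if the error is too large, excess type I error if it is too small.

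**Working it through.** **The plan's power figure.** 20% of 444.3 is 88.86 PU. Taking 55.1 PU as the SD at each occasion with zero correlation, the SD of a paired difference is √2 × 55.1 = 77.9 PU, and its standard error with 16 participants is 77.9/4 = 19.5 PU. A two-sided paired t-test (15 df) has power 98.9% at 0.05 and 95.7% at 0.05/3, against the stated 98% and 96%. The figures are reproduced to within a point. One-sided, as the SAP tests, they are 99.7% and 98.1%.

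**Design.** Protocol Table 5-1: 4 sequences × 4 participants, 4 periods, 2 times, 128 values per method and concentration. Participants, periods and treatment-by-time cells use 26 parameters, leaving 102 residual df. With 3 h only: 64 values, 22 parameters, 42 df. One-sided critical t at 0.05/3: 2.157 and 2.200.

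**The estimate.** With complete data each 3 h contrast puts ±1/16 on 3 h values and 0 on every 24 h value. Its variance is 2/16 = 0.125 times the residual variance in both models.

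**The error term.** Write σ² for the 3 h residual variance, F for participant-by-forearm variance and P for participant-by-period variance shared by both times.

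- Forearm: 15 df, each carrying 4F, give 60F/102 = 0.588F in the pooled mean square. In the true contrast variance F has coefficient 0.
- Shared period variation: 42 df, each carrying 2P, give 84P/102 = 0.824P. In the true contrast variance P has coefficient 1.
- Unequal variances: the pooled mean square averages the 3 h and 24 h variances; the contrast needs only the 3 h one.

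The ratio of reported to true standard error is the square root of pooled mean square over true variance. Sizes and powers below are simulated. All variance ratios are assumptions.

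| Assumed departure | SE ratio | One-sided size (nominal 1.67%) |
|---|---|---|
| None | 1.00 | 1.67% |
| F = 0.25σ² | √1.147 = 1.07 | 1.15% |
| F = 0.5σ² | √1.294 = 1.14 | 0.8% |
| F = σ² | √1.588 = 1.26 | 0.4% |
| P = σ² | √(1.824/2) = 0.955 | about 2.1% |
| 24 h variance halved | √0.75 = 0.87 | about 3.2% |
| 24 h variance doubled | √1.5 = 1.22 | 0.5% |
| F = 0.25σ² and P = σ² | √(1.971/2) = 0.99 | about 1.7% |

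The 3 h-only test has size 1.6% to 1.7% throughout. If 55.1 PU is the residual SD, the three forearm ratios mean left-right differences with SD √(2F) = 39, 55 and 78 PU, or 9%, 12% and 18% of 444.3 PU.

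**Power under a forearm effect alone** (residual SD 55.1 PU, one-sided 0.05/3):

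| Reduction | Pooled, F = 0 | F = 0.25σ² | F = 0.5σ² | F = σ² | 3 h only |
|---|---|---|---|---|---|
| 20% (planned) | 99.1% | 98.7% | 98.1% | 96.4% | 99.0% |
| 15% | 89.6% | 86.5% | 83.1% | 75.6% | 88.5% |
| 10% | 55.2% | 49.1% | 43.6% | 33.8% | 53.7% |

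**What pooling gains.** With none of the departures, the extra df are worth at most 1.5 points (66.4% against 64.9%, by noncentral t).

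**The case against.** The strongest reply is that no forearm effect has been shown. The ratios above are assumed, the PU translation is on the absolute scale, and the tested variable is percentage change from each site's own pre-challenge value, which may remove part of a proportional difference between arms. At the planned 20% reduction even the largest forearm ratio tabulated leaves 96.4%, level with the SAP's stated 96%; the large losses occur at reductions the trial was not sized for. If pooling's assumptions hold, the SAP model is slightly better. All of this stands. It limits the point to a cheap improvement.

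A reader might infer that the pooled test is simply conservative, so that type I error is protected and only power is lost. That holds only if a forearm effect is the sole departure. Shared period variation or a smaller 24 h variance pushes the other way, and the effects can cancel, as the last row of the first table shows.

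A reader might also infer that the 24 h data contribute nothing at all. That is exact only for the estimate with complete data. They add df, and SAP 10.3 keeps drop-outs who have placebo and one active treatment. In one assumed pattern of three drop-outs, with between-participant variance equal to the residual, the 24 h values received weights up to 0.009 and reduced the contrast variance by about 0.5% (0.12998 against 0.13066).

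**Conclusion.** The point holds as one of robustness. The primary standard error depends on three variance conditions, none supported by the documents, while the 24 h values contribute nothing to the complete-data estimate in return. Its error may be too large or too small, and the documents do not settle which. At the planned effect the primary conclusion is not threatened; the choice matters more if one of the three doses, each tested on its own, achieves nearer 10% to 15%.

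The power figures assume that 55.1 PU is the within-participant residual SD and that planning on absolute flow carries over to percentage change. If 55.1 PU already includes forearm variation, the residual is smaller and the loss at 20% smaller still.

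A separate documentation note carries no weight in this verdict. Protocol 10.3.3 says "Mixed-effect model for repeated measure (MMRM) will be used to evaluate the primary endpoint including covariates such as treatment, period, carry-over, and sequence"; the SAP model has no carry-over term. SAP 3.0 says that "where considerations are substantially different, they will be so identified", and SAP 7.1 says "There are no changes from the protocol". A reader might infer a substantive flaw, but the protocol's list is illustrative, Table 5-1 contains each of the 12 ordered treatment pairs once, and the schedule places doses 14 days apart.

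**What to change.** In SAP 17.2.2, run the primary test on 3 h data only and analyse 24 h separately in the same way: `by CAconc method time; model pchg = trtan period seq; random subject(seq);`, with `lsmeans trtan`. This moves time to the BY statement and drops the two time terms. Residual df fall from 102 to 42, which costs at most about 1.5 power points, and only if all of pooling's assumptions hold. With missing data the estimates may differ slightly from the joint model's. The change also fits protocol 10.3.3, which treats 24 h as a further, similar analysis.

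If a joint model is preferred, it needs `time*subject(seq)`, a participant-by-period term and time-specific residual variances to give the same protection. Adding `time*subject(seq)` alone (87 df) handles the forearm but not unequal variances: size is still about 3.2% with the 24 h variance halved.

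For the documentation, add one sentence to SAP 7.1 stating that the carry-over term named in protocol 10.3.3 is not fitted. Fitting it as a sensitivity analysis would also do; on 3 h data it raises the standard error by about 5% (√(0.1375/0.125) = 1.049) and leaves 39 df.

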5.4 Study Hypothesis

The null hypothesis H_0 is that there is no decrease in CA-induced DBF relative to placebo measured by laser Doppler Imaging (LDI) at 3 hours post-dose at an α level of (0.05/3), one-sided. Bonferroni adjustment is used to account for the three comparisons (dose levels) versus placebo.

If the null hypothesis is rejected for any of the dose levels, the alternative hypothesis, i.e. there is a decrease for this dose level, will be accepted.

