6.0 Study Design

This is a Phase 1 randomized, double-blind, placebo-controlled, 4-way crossover study of LY3526318 in healthy female participants.

All participants will have 2 screening visits with the first to evaluate the health of the participant and the second visit to undergo an LDI assessment to ensure a response of at least 100% increase in DBF between pre- and post-CA challenge. Following a screening period of up to 28 days, eligible participants will be confined to the clinical research unit from Day 1 until all assessments are completed on Day 2 of each dosing period.

As summarized in [Table 1](#), each participant will be randomly assigned to 1 of 4 treatment sequences, with a ratio of 3 LY3526318: 1 placebo. Each participant will receive 3 doses of LY3526318 and 1 dose of placebo in a crossover manner, with at least 6 days of washout between doses. The planned dose levels of LY3526318 are anticipated not to exceed the maximum administered dose in the SAD portion of Study CVAA.

Table 1 Treatment Sequence

Sequence	N	Period 1	Period 2	Period 3	Period 4
P132	4	P	D1	D3	D2
12P3	4	D1	D2	P	D3
231P	4	D2	D3	D1	P
3P21	4	D3	P	D2	D1

During each visit (screening and study periods), each patient will undergo at least 30 minutes acclimatization and placement of 3 rubber O-rings on the volar surface of the forearm. Prior to study drug administration, a pre-drug DBF will be collected without CA. For each time point following study drug administration, pre-CA measurements will be performed for the areas defined by the rings within 10 minutes before CA application. After the pre-CA measurements, a 20 μ L topical dose of 10% CA will be applied in the proximal O-ring of the participant's forearm. Using the same procedure, a 20 μ L topical dose of 3% CA will be applied in the medial ring, followed by a 20 μ L topical dose of the vehicle solution to the distal ring. LDI/LSCI measurements will again be performed approximately 20 minutes after CA and vehicle applications. Specific details of the procedure will be agreed upon and documented between the sponsor and investigator and research staff operating the equipment.

All assessments will be performed as defined in Schedule of Activities ([Appendix 2: Schedule of Assessments](#)).

All participants will attend a safety follow-up visit about 7 days following the last dose of study drug.

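### The one-sided 0.05/3 level is sized for three dose comparisons but applied at each of two cinnamaldehyde (CA) concentrations, and no primary concentration is named

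*SAP*

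**What the plan says.** - **The level and what it covers.** SAP 5.4 places the null hypothesis "at 3 hours post-dose at an α level of (0.05/3), one-sided", and explains the divisor: "Bonferroni adjustment is used to account for the three comparisons (dose levels) versus placebo". SAP 9.4.3 repeats the level: "Significance testing will be 1-sided at the significance level of 0.05/3 for the primary statistical analysis".
- **The decision rule.** SAP 17.2.2 fits a separate model for each imaging method and CA concentration. It calls a result significant when P is below 0.05/3, and states the scope as "For each of the active dose levels and CA concentrations, a decrease relative to placebo of the percentage change".
- **Two active concentrations.** SAP 6.0 puts 10% CA in the proximal ring, and a "topical dose of 3% CA will be applied in the medial ring". The distal ring receives vehicle.
- **What is primary.** Protocol 10.3.3 says "The primary endpoint is the percent change from pre-CA to CA-induced DBF as measured by LDI", compared with placebo at 3 hours. For the output tables, SAP 17.2.2 says "it will be indicated that the result for LDI, 3 hours post-dose is the primary end point". Neither gives a concentration, and nor do protocol Table 4-1 and SAP 5.1.1.
- **Where 10% CA is singled out.** Only in the sample-size text, protocol 10.1 and SAP 6.1: "The power calculation used 10% CA-induced absolute DBF in comparison between LY3526318 and placebo arms".

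**The concern.** The two SAP sections disagree on how many tests the 0.05/3 level covers. SAP 5.4 counts three. SAP 17.2.2 applies it to three doses at each of two concentrations, which is six tests for LDI at 3 hours. No ordering or gatekeeping between the concentrations is given.

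The first consequence is that the primary decision is not fixed. SAP 5.4 accepts the alternative for any dose whose null is rejected. Suppose a dose passes at 3% CA and fails at 10% CA. One analyst could report target engagement and another could report none, from the same data and the same plan, and the choice could be made after unblinding.

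The second consequence is the error rate. If either concentration can carry the claim, the chance of at least one false claim is no longer held at one-sided 5%.

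**Working it through.** **Inputs from the documents**
- Per-test level: 0.05/3 = 0.01667, one-sided (SAP 5.4, 9.4.3).
- Design: 4 sequences × 4 participants, 4 periods (SAP Table 1).
- Sizing: placebo mean 444.3 PU, SD 55.1 PU, 20% reduction, n = 16, paired t-test (SAP 6.1).

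**Assumptions**
- Correlation between residuals at the 10% and 3% sites: not given, so 0, 0.5, 0.7 and 0.9 are shown.
- Correlation within a participant between treatment periods, needed for the paired SD: not given, so 0 is used, with 0.25 as a variant.

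**Step 1. Reproduce the plan's power**
- Difference = 0.20 × 444.3 = 88.86 PU.
- SD of the paired difference = 55.1 × √(2(1 − r)) = 77.92 PU at r = 0.
- Noncentrality = 88.86 / 77.92 × √16 = 4.56, with 15 degrees of freedom.
- Two-sided power is 98.9% at 0.05 and 95.7% at 0.05/3. The SAP prints 98% and 96%, so these agree within one point.
- One-sided power is 99.7% and 98.1%. The printed figures are therefore closer to a two-sided test, although the SAP tests one-sided.

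**Step 2. Count the tests for LDI at 3 hours**
- One concentration: 3 tests; Bonferroni bound 3 × 0.05/3 = 5%.
- Two concentrations: 3 × 2 = 6 tests; bound 6 × 0.05/3 = 10%. If all six were independent, 1 − (1 − 0.01667)^6 = 9.6%.

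**Step 3. Allow for the shared placebo and correlated sites**

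100,000 null trials were simulated per scenario on the Table 1 design, with participant, period and treatment effects and one-sided P values. Two models were run: the SAP's joint 3 h/24 h model (102 residual degrees of freedom, independent residuals as that model assumes) and a 3 h-only ANOVA (42). Participant was fitted as a fixed effect, which gives the same within-participant contrasts when data are complete and balanced. One concentration alone gives about 4.2%.

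| Chance of a false claim | r = 0 | r = 0.5 | r = 0.7 | r = 0.9 |
|---|---|---|---|---|
| Six tests at 0.05/3, joint model | 8.3% | 7.6% | 7.1% | 5.9% |
| Six tests at 0.05/3, 3 h only | 8.3% | 7.7% | 7.1% | 6.1% |
| Claim resting on 3% CA alone, at 0.05/3 | 4.0% | 3.4% | 2.9% | 1.8% |
| Six tests at 0.05/6 | 4.3% | 4.1% | 3.8% | 3.3% |

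A separate multivariate normal calculation, with dose contrasts correlated 0.5 through the shared placebo, gives 8.4%, 7.7%, 7.1% and 6.0% for six tests at 0.05/3. Only a correlation of 1 brings this back to the single-concentration 4.3%.

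**Step 4. Power if both concentrations are kept (10% CA, one-sided, n = 16)**
- r = 0: 98.1% at 0.05/3 and 95.7% at 0.05/6.
- r = 0.25 (SD of the difference 67.5 PU): 99.7% and 99.0%.
- No mean or SD is given for 3% CA, so its power cannot be computed.

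**The case against.** **10% CA is implied.** The sample-size text ties the primary endpoint to 10% CA and introduces the 0.05/3 adjustment in the same paragraph, and three comparisons fit only one concentration. Most readers would guess 10%. But this is an inference. The calculation uses absolute flow while the tested variable is percentage change, so it does not define the tested endpoint, and the explicit rule in 17.2.2 covers both concentrations.

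**The 17.2.2 sentence is a general labelling rule.** It restricts neither method nor time point; read literally it covers 3 × 2 × 2 × 2 = 24 tests, including exploratory ones. That is fair, and LSCI and 24 h are left out of the count because the plan ranks them as secondary or exploratory. The plan ranks the two concentrations nowhere.

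**The P value might be two-sided.** The SAP code shows no one-sided option. A two-sided P below 0.05/3 in the right direction equals one-sided 0.05/6, and the inflation disappears. However, SAP 5.4 and 9.4.3 both specify one-sided testing.

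**Power is not free.** If two-sided testing is the basis, moving to 0.05/6 takes power from 95.7% to 91.6%. All these powers concern absolute flow, and the documents give no SD for percentage change. Both caveats stand.

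**The setting is modest.** This is a 16-participant Phase 1 pharmacodynamic study, the inflation is at most a doubling, and results at both concentrations will be reported. This limits the practical harm but does not supply the missing decision rule.

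**Conclusion.** The concern holds. The main defect is that the plan does not say which tests decide its primary objective, and its two statements about the 0.05/3 level conflict. This follows from the text and needs no assumption.

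The error inflation is conditional. Within one concentration the Bonferroni correction is right. If both concentrations count and P values are one-sided as stated, the family-wise error for LDI at 3 hours exceeds 5% at every site correlation examined from 0 to 0.9, with the doubled Bonferroni bound as the ceiling. Because this is the study's only stated hypothesis test, it should be settled before unblinding, even though the consequences in a Phase 1 study are limited.

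**What to change.** Choose one of the following and write it into SAP 5.1.1, 5.4 and 17.2.2.

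- **A. One primary concentration.** Name LDI, 3 hours, 10% CA as the primary endpoint, since that is the concentration used for sizing. Restrict the 0.05/3 rule to its three dose-versus-placebo tests and label the 3% CA results supportive. The family-wise bound is then 5% and the power stays as planned. The cost is that a result seen only at 3% CA cannot carry the primary claim.
- **B. Both concentrations primary.** Say so, and test each of the six comparisons at one-sided 0.05/6. The cost for 10% CA is the power loss in Step 4, about 2.4 points at r = 0 (98.1% − 95.7%). Power for 3% CA would need inputs that the documents do not contain.

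A is the simpler choice. Either needs about one sentence per section and no new data or model. SAP 3.0 gives the SAP precedence over the protocol's statistical text, so the SAP change can suffice; matching wording in protocol 10.3.3 would keep the two aligned, at the cost of an amendment.
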